6. ASSESSMENT AND REPORTING OF ADVERSE EVENTS

Patients will be monitored in the office for three hours to assess for any side effects, which may include worsening tremors, voice changing or worsening rigidity.

***Serious Adverse Events (SAE):** Adverse Events will be monitored and logged and reported to the IRB.*

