PROTOCOL

Official Title: Deep brain stimulation effects on gait and balance in patients with Parkinson's disease

PI: [name] [name]

Document Date: January 4, 2016

NCT Number: NCT02022735

1. STUDY DESIGN AND SCHEMA:

Gait and balance problems are dopamine resistant features of Parkinson's disease (PD).

Deep brain stimulation of sub-thalamic nucleus (STN-DBS) is an established surgical method that improves motor symptoms and gait in PD, however it may produce unexpected freezing of gait and balance problems in some patients, presumably due to overstimulation and gait incoordination. The aim of this study is to identify the differential effects of unilateral STN stimulation versus bilateral stimulation on gait kinematics in patients with PD and associated gait dysfunction.

2. BACKGROUND AND RATIONALE :

Freezing of gait (FOG) and walking difficulties represent perhaps the most difficult challenges in the treatment of Parkinson's disease (PD). PD patients experience frequent difficulty initiating walking, shuffling and postural instability (Vu, Nutt et al. 2012). In spite of dopaminergic therapy, walking difficulties continue to progress and only rarely do non-dopaminergic treatments provide benefit. Deep brain stimulation of sub-thalamic nucleus (STN-DBS) improves motor scores, walking and FOG (St George, Nutt et al. 2010). In some patients, even after appropriate fine tuning of programming, walking and balance continue to be a problem. One explanation can be the progression of the disease, however in some cases the FOG appears soon after the DBS. This has been attributed to overstimulation and perhaps asymmetric stimulation in the networks involved in gait

control. Several studies have looked at the parameters of stimulation and have concluded that reducing the frequency of stimulation would ameliorate walking difficulties (Fasano, Herzog et al. 2011). Similarly, reducing the amplitude contralateral to the most affected side is associated with less FOG (Moreau, Defebvre et al. 2008).

A growing body of literature suggests that right-hemisphere circuitry seems to be more affected than the left in patients with FOG (Fling, Cohen et al. 2013) and that patients with worse symptoms on the left are more likely to develop postural instability gait dysfunction (PIGD) (Giladi, McDermott et al. 2001)

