3. OBJECTIVES

In this study we aim to evaluate the effects of differential STN stimulation on walking. We hypothesize that in patients with FOG, unilateral stimulation on the most affected hemisphere will ameliorate walking in a higher degree than bilateral stimulation. Functional asymmetry of STN was shown before by other studies (Castrioto, Meaney et al. 2011) and is thought that unilateral STN stimulation has effects that are similar with bilateral STN on UPDRS motor scores, effect called dominant STN. Since the effects of unilateral stimulation on walking are not completely understood, we plan to determine if unilateral stimulation has differential effects on gait kinematics.

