5. MEASUREMENTS AND EVALUATION

This study is meant to see if there is improvement in gait or freezing of gait after changes in the stimulation parameters.

- In the first part of the study subjects (1 visit) will be randomly assigned to four different stimulation parameters: both stimulators ON, both stimulators off, right stimulator ON, left stimulator ON. We will assess participants' gait using clinical scales as well as wearable sensors attached to the body. Assessments will be done one hour after each change in the stimulation parameters.
- In the second part of the study that participants may be asked to participate in, changes in the frequency of stimulation and contact stimulation will be performed. Four different stimulation settings will be tested. In this part evaluations will be done.

PART 1

Screening: At this visit, the study investigator will discuss the details of the research study and the consent form with the study participant.

The following procedures will also be completed:

- Sign informed consent form.
- Collection of a complete medical history and a neurological exam.
- United Parkinson's disease rating scale (UPDRS) will be performed by a Movement Disorder Specialist to assess the severity of Parkinson's disease.

- Timed Up and Go test (TUG) - a mobility test that is used to measure the basic mobility skills of people who are elderly or have neurological conditions such as PD and it includes a sit-to-stand component as well as walking 3m, turning and returning to the chair.
- Freezing of Gait Questionnaire (FOGQ) which is a self-report questionnaire consisting of 16 items regarding falls and walking problems.
- Gait analysis using wearable sensors (Mobility Lab) to measure the walking speed and step length.

If study subjects meet the eligibility criteria, they will be asked to sign the informed consent and asked to come to clinic for part 1 or for part 2 of the study without taking their Parkinson's medication for 12 hours.

Visit 1 Changes to the DBS stimulator will be done every 60 minutes for 4 hours in a random order.

- Bilateral stimulators ON, bilateral stimulators OFF, Right ON-Left OFF, Right OFF-Left ON.
- UPDRS scale
- Gait analysis using wearable sensors (Mobility Lab) to measure the walking speed and step length.

This visit will take about 5 hours. At the end of the visit study participants will go home with their initial settings.

PART 2

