Screening: At this visit, the study investigator will discuss the details of the research study.

The following procedures will be completed:

- United Parkinson's disease rating scale (UPDRS) will be performed by a Movement Disorder Specialist to assess the severity of their Parkinson's disease.

- Timed Up and Go test (TUG) - a mobility test that is used to measure the basic mobility skills of people who are elderly or have neurological conditions such as PD that includes a sit-to-stand component as well as walking 3m, turning and returning to the chair.
- Freezing of Gait Questionnaire (FOGQ) which is a self-report questionnaire consisting of 16 items regarding falls and walking problems.
- Gait analysis using wearable sensors (Mobility Lab) to measure the walking speed and step length.
- The PI will review the medical records to assess if precise localization of the electrode contacts can be done using the CT scan that was performed post-operatively and will decide if an MRI of the brain is necessary to perform.

Visits 1, 2, 3 and 4

During these visits the stimulation settings will be changed to one of the following conditions: Low frequency stimulation-dorsal STN, Low frequency stimulation- ventral STN, High frequency stimulation- dorsal STN, High frequency stimulation –ventral STN

After each change the following tests will be performed:

- United Parkinson's disease rating scale (UPDRS) will be performed by a Movement Disorder Specialist to assess the severity of Parkinson's disease.
- Timed Up and go test (TUG) - a mobility test that is used to measure the basic mobility skills of people who are elderly or have neurological conditions such as PD and it includes a sit-to-stand component as well as walking 3m, turning and returning to the chair.
- Freezing of Gait Questionnaire (FOGQ) which is a self-report questionnaire consisting of 16 items regarding falls and walking problems.
- Gait analysis using wearable sensors (Mobility Lab) to measure the walking speed and step length.
- Clinical Global Improvement Scale

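### Does the unspecified side-effect monitoring spoil the planned adverse event frequencies?

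*Combined protocol and SAP*

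**What the plan says.** Section 6 gives safety monitoring two sentences. Each patient is "monitored in the office for three hours to assess for any side effects, which may include worsening tremors, voice changing or worsening rigidity", and "Adverse Events will be monitored and logged and reported to the IRB". Neither names a visit, a study part, a start time or a state against which worsening is judged. Section 7 lists adverse event frequencies among its descriptive outputs, alongside demographics, velocity, stride length, TUG and UPDRS. It gives no denominator and no breakdown.

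The setting for this is in Section 5. Participants attend "without taking their Parkinson's medication for 12 hours". Part 1 tests "both stimulators ON, both stimulators off, right stimulator ON, left stimulator ON", and for Visit 1 the schedule reads "Changes to the DBS stimulator will be done every 60 minutes for 4 hours in a random order", within a visit of about five hours. The UPDRS and the sensor-based gait analysis are listed for that visit, and Section 5 places assessments one hour after each change. For Part 2, "During these visits the stimulation settings will be changed to one of the following conditions"; the conditions combine low or high frequency with dorsal or ventral STN, and no visit length is given.

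Two statements bear on what to expect with stimulation off. Section 1 says STN-DBS "is an established surgical method that improves motor symptoms and gait in PD". Section 3 reports the view that "unilateral STN stimulation has effects that are similar with bilateral STN on UPDRS motor scores".

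**The concern.** Part 1 withdraws treatment on purpose. If stimulation improves motor signs, as Section 1 says, tremor or rigidity may well worsen when it is removed, and Section 6 names exactly those signs as possible side effects. A single adverse event frequency could then mix unintended effects of stimulation with the foreseeable effect of having it off.

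The missing reference state adds to this. The same observation might count as worsening against both stimulators on, but not against the preceding setting or against screening, where no medication withdrawal is stated. Because the order is random, the preceding setting differs between participants.

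The three-hour period also looks too short beside four hours of test settings. At stake is how the safety summary is read. The gait results do not depend on it.

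**Working it through.** The protocol gives no adverse event rate, so there is no stated figure to reproduce. The checks use the stated times and the possible setting orders.

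**Exposure (Section 5, Part 1).** Four settings of 60 minutes give 4 × 60 = 240 minutes. At least one stimulator is off in 3 of 4 settings (180 of 240 minutes, 75%). Both are off in 1 of 4 (60 of 240 minutes, 25%). If unilateral and bilateral stimulation have similar motor effects, as Section 3 suggests, the smaller share is the relevant one. Medication is withheld throughout the visit, so it does not differ between settings.

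**Dependence on the reference state.** There are 4! = 24 orders, taken as equally likely. Suppose stimulation has no side effects at all, and every participant shows, and has logged, each worsening. That is an assumption: the protocol gives no response rate, time course or logging threshold.

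*Case A: only both-off is worse.*
- Against both on: an event in 24 of 24 orders (100%).
- Against the preceding setting, with no predecessor for the first: no event when both-off comes first, which is 3! = 6 orders. That leaves 18/24 = 75%.
- Against the preceding setting, with arrival on both on: both-off always follows a better state, so 24/24 = 100%.

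*Case B: graded worsening from both on, through one unilateral setting and then the other, to both off.*
- Against both on: 3 events in every order.
- Against the preceding setting, counting the three changes between settings: 0, 1, 2 and 3 events in 1, 11, 11 and 1 orders. Mean = (0 + 11 + 22 + 3)/24 = 36/24 = 1.5.
- Against the preceding setting, adding the change from an arrival state of both on: 1, 2 and 3 events in 2, 14 and 8 orders. Mean = (2 + 28 + 24)/24 = 54/24 = 2.25.

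The protocol does not state the arrival setting. It does say that participants leave on their initial settings, and a change every 60 minutes for four hours fits four changes better than three. With arrival on both on, the contrast in Case A disappears and the one in Case B narrows from 3 against 1.5 to 3 against 2.25. These figures show what each assumption implies and are not estimates of distortion in this trial.

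**Monitoring period.** If the three hours are a single period at Part 1 Visit 1, they are at least 240 − 180 = 60 minutes shorter than the sequence. If that period began with the first setting, the both-off hour would fall last, outside it, in 6 of 24 orders (25%). If the three hours refer to Part 2, there is nothing to compare them with, because no visit length is given. Section 6 does not say which applies. Its separate statement that adverse events are monitored and logged carries no time limit, so no event is shown to go unrecorded.

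**From side effect to frequency.** Section 6 says what side effects may include. Its next sentence and Section 7 speak of adverse events. No sentence equates the two or requires expected off-stimulation worsening to be counted. Section 7 does not prescribe one figure pooled over settings or parts.

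**The case for a change.** The strongest case for a change is that leaving attribution to unstated judgement is itself the weakness. Section 6 puts worsening tremor and rigidity under the adverse event heading with no exclusion, and adverse event frequency is the first output named in Section 7. A table by setting can be built later only if the setting at onset can be recovered. Even then it does not settle what worsening was judged against. The remedy would be cheap: a few sentences, two log fields and one table.

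Part of this stands. The reference state is not written down, expected worsening could be logged, and a by-setting table would not fully answer the question of comparator.

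The stronger claims do not stand. That such worsening *would* count is a reading of undefined terms. That the causes *cannot* be separated overlooks the design: settings change hourly in an assigned order, so a logged onset time identifies the setting in force, and the UPDRS is planned within the same visit. A short protocol that does not describe its log fields does not show that they are absent. One proposed remedy, grouping every setting with a stimulator off apart from both on, would pool unilateral stimulation, the condition the hypothesis favours, with complete withdrawal. That mixes the causes it is meant to separate.

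**Conclusion.** This is missing detail that analysts can fill sensibly, and no change to the plan follows. The output concerned is one descriptive frequency, with no test, threshold or decision rule attached. Each Part 1 participant is scheduled for all four settings, so the natural summary is by setting and by study part, with the both-off and the two unilateral settings shown separately. Nothing in Section 7 stands in the way, and a reader of that table can see whether worsening gathers where stimulation is off.

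No defensible size can be put on the concern. The 75% against 100% contrast depends on giving the first setting no predecessor, and it vanishes if participants arrive with both stimulators on. The 60-minute difference is a contradiction only if the three hours mean one period at Part 1 Visit 1, which the text does not establish. If that is what was intended, Sections 5 and 6 would have to be reconciled by the investigator.

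The conclusion assumes that the log records onset time or setting, and that the report says how worsening was judged. If neither happened, the adverse event summary would be harder to interpret, but the gait and UPDRS summaries would be unaffected.

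### Section 6 does not prompt staff for freezing, balance loss or falls, and Section 7 does not report adverse events by stimulator setting, so Part 1 may not show how these events differ between settings

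*Combined protocol and SAP*

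**What the plan says.** Section 6 sets the purpose of monitoring as the detection of side effects of any kind, "which may include worsening tremors, voice changing or worsening rigidity". It states that "Patients will be monitored in the office for three hours" and that "Adverse Events will be monitored and logged and reported to the IRB". It gives no definition of an adverse event and no method for asking about one.

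Section 1 says of stimulation of the subthalamic nucleus that "it may produce unexpected freezing of gait and balance problems in some patients, presumably due to overstimulation and gait incoordination". Section 4 enrols patients who developed trouble walking in the months after surgery.

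Under Section 5, participants are "asked to come to clinic for part 1 or for part 2 of the study without taking their Parkinson's medication for 12 hours". Part 1 Visit 1 then applies, in random order, "Bilateral stimulators ON, bilateral stimulators OFF, Right ON-Left OFF, Right OFF-Left ON", with hourly changes over four hours in a visit of about five. The measurements listed for that visit are the UPDRS and sensor gait analysis. Section 5 also says that the study looks for improvement in gait or in freezing. The Freezing of Gait Questionnaire (FOGQ), which the protocol describes as covering falls and walking problems, is listed at both screenings and after each change in Part 2.

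Section 7 plans descriptive summaries: adverse event frequencies, demographics, velocity, stride length, TUG and UPDRS.

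**The concern.** The effects that motivate the study, freezing and balance problems, are missing from the examples given to the people watching for side effects. Falls are missing too. The protocol does not name falls as an effect of stimulation, but they are a reasonable inferred risk in people with walking difficulty who are tested after 12 hours without medication.

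Unprompted capture leaves each assessor to decide whether a near-fall or a freezing episode during a gait test is an adverse event, part of the test, or neither. If the log is then summarised without reference to setting, Part 1 could show faster walking at one setting and be unable to say whether freezing or falls were more or less frequent there. That comparison bears directly on the study's question about one-sided against two-sided stimulation.

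**Working it through.** The plan has no figure of its own to reproduce on this point. The check compares the sections and adds two short pieces of arithmetic.

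**1. Named effects against named examples.** Section 1 names freezing and balance problems. Section 6 names tremor, voice and rigidity. Examples in Section 6 that are a freezing, balance or fall event: 0 of 3.

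**2. Instruments by visit (Section 5).**

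| Visit | FOGQ listed? | Other measures listed |
|---|---|---|
| Part 1 screening | Yes | UPDRS, TUG, sensors |
| Part 1 Visit 1 (four settings) | No | UPDRS, sensors |
| Part 2 screening | Yes | UPDRS, TUG, sensors |
| Part 2 Visits 1 to 4 | Yes | UPDRS, TUG, sensors, global improvement scale |

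The one visit at which the four Part 1 settings are compared is also the only one without the FOGQ. The sensor outputs described there are speed and step length. Neither is a count of freezing episodes or falls.

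**3. Route to the analysis (Section 7).** The FOGQ is not among the variables to be summarised. The adverse event frequencies are therefore the only planned summary in which a fall would plainly appear, and Section 7 does not say that they will be split by setting.

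**4. Medication state.** Assume that changes start on arrival and that no dose is taken during the visit; the documents state neither. Assessments follow each change by one hour, so the first comes about 12 + 1 = 13 hours after the last dose. The visit ends at about 12 + 5 = 17 hours.

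**5. Monitoring period against test period.**
- Test period: 4 settings × 60 min = 240 min.
- Stated monitoring: 3 h = 180 min.
- Least possible shortfall: 240 − 180 = 60 min, or 60/240 = 25% of the test period, wherever the three hours are placed.
- If the three hours start at the first change, they end as the fourth setting begins, and that whole setting is outside them.
- If they start at the last change, 180 min into the sequence, they end at 180 + 180 = 360 min, or 6 h, which exceeds a visit of about 5 h.
- If they refer only to Part 2, no monitoring period is stated for Part 1.

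**The case against.** The strongest reply is that Section 6 is open. It asks for any side effects, introduces its three terms as possibilities, and requires adverse events to be logged and reported. A fall is therefore within planned capture and within the Section 7 frequencies. This stands. A reader might infer that falls or freezing are excluded, or that staff are told to look only for three signs; the text supports neither. What remains is that capture is unprompted and not linked to a setting.

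Second, gait is the outcome and is assessed at every setting, so deterioration will be seen. This stands in part. Worse walking would show in speed and step length, but those measures do not count episodes. The objection also raises a fair warning: if worsened freezing becomes an adverse event with no further rule, one phenomenon could be counted both as outcome and as harm. The fix has to deal with that.

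Three other stronger readings should be resisted:
- That nothing at Part 1 Visit 1 asks about falls. The UPDRS is done there and the documents do not list its items, so this cannot be shown. One can say only that no such item is described.
- That falls with both stimulators off are the protocol's own stated or leading hazard. Section 1 names freezing and balance problems, presumes overstimulation as the cause, and ranks no hazards. Risk with stimulation off is an inference from the population and the medication withdrawal.
- That events will go unlogged, or that a setting will be recommended on mean speed. The plan is descriptive, and Part 1 patients leave on their initial settings.

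**Conclusion.** The point holds as a gap in prompting and in reporting by setting, not as an exclusion of these events. None of the three examples in Section 6 covers the effects named in Section 1. The four-setting comparison in Part 1 has no described record of freezing, balance loss or falls, and Section 7 neither splits adverse events by setting nor summarises the FOGQ. The number of events at stake cannot be sized, because the documents give no sample size and no event rate.

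The conclusion rests on one inference, that falls are a plausible risk in these patients off medication, and on the lists in Section 5 being complete. It should be acted on because the remedy changes what Part 1 can report, and not only how Section 6 reads. The conflict between three hours of monitoring and four hours of setting changes follows from the text alone, if the three hours are meant to cover the Part 1 visit.

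**What to change.** - **Section 6.** Add falls, near-falls and observed freezing or balance loss to the examples. Define near-fall so that a loss of balance is recorded in one place only, for instance as any loss of balance that does not end in a fall.
- **Section 5.** Have the assessor already present record yes/no and number for each event at every Part 1 and Part 2 setting, from one setting change to the next. For the last Part 1 setting, count to the return to initial settings. The Part 1 periods are about 60 minutes each, so counts can be compared directly. For Part 2, state what period the count covers, because the documents do not say how long a setting is kept.
- **Section 7.** Report the counts by setting beside walking speed. Report freezing episodes as a gait outcome, and falls and near-falls as adverse events, so that nothing is counted twice.
- **Sections 5 and 6.** Reconcile the three-hour monitoring period with the four hours of setting changes, and say which visits the period applies to.

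The cost is a few sentences and a few fields per setting, with no extra visit, procedure or staff. The downside is a higher reported event count, since prompted recording finds events that unprompted logging would miss.
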